8.6.3. Laboratory Evaluations

Selected laboratory data (using conventional units) will be summarized using only observed data. Absolute values and changes from baseline at all scheduled visits will be summarized.

Graded laboratory abnormalities will be defined using the grading scheme defined in Grading of laboratory abnormalities attached in [Appendix 5](#).

Incidence of treatment-emergent laboratory abnormalities, defined as values that increase at least 1 toxicity grade from baseline at any time post baseline up to and including the date of last dose of study drug plus 30 days, will be summarized by treatment. If baseline data are missing, then any graded abnormality (i.e., at least a Grade 1) will be considered treatment emergent. The maximum post baseline toxicity grade will be summarized by laboratory parameter.

Laboratory abnormalities that occur before the first dose of study drug or after the last dose of study drug plus 30 days will be included in a data listing.

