3. GENERAL CONSIDERATIONS FOR DATA ANALYSES

The Final Analysis will include two sets of analysis: randomized phase analysis and all B/F/TAF analysis. All table summaries in this final analysis will be based on data included in the All B/F/TAF analysis (eg, data collected during the study period when participants were on B/F/TAF). Randomized phase analysis (eg, including data collected during double-blind phase when participants were on the double-blind study drug) and the corresponding analysis window defined in Section 3.8, will be used to support applicable listings where data collected from the double-blind phase are indicated. The wording of randomized phase or double-blind phase might be used interchangeably throughout the SAP and in the TFLs.

Randomized Phase Analysis:

- For subjects who are never treated in the extension phase of the study including those who prematurely discontinue the randomized study drug or who complete the randomized study drug and do not receive any dose of B/F/TAF in the extension phase, all available data will be included in the randomized phase analysis.
- For subjects who complete the randomized phase and receive at least 1 dose of B/F/TAF in the extension phase, the randomized phase analysis will include (1) all available AE, concomitant medication, pregnancy, and death data collected prior to the extension phase first dose date; (2) all available other data, such as laboratory, vital sign, electrocardiogram (ECG), collected on or prior to the extension phase first dose date.

All B/F/TAF Analysis:

- For subjects who receive B/F/TAF in the randomized phase, all available data for subjects who actually receive B/F/TAF in the randomized phase will be included.
- For subjects who actually receive DTG+F/TAF in the randomized phase and receive at least 1 dose of B/F/TAF in the extension phase, (1) all available AE, concomitant medication, pregnancy, and death data with start date **on or after** the first dose date of B/F/TAF in the extension phase and (2) all available other data, such as laboratory, vital sign, and ECG data, collected **after** the first dose date of B/F/TAF in the extension phase will be included. The data collected **on or prior to** the first dose date of B/F/TAF will be used to derive the baseline value for the all B/F/TAF analysis.

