7.2.2. Graded Laboratory Values

The Gilead Grading Scale for Severity of Adverse Events and Laboratory Abnormalities will be used for assigning toxicity grades (0 to 4) to laboratory results for analysis. Grade 0 includes all values that do not meet the criteria for an abnormality of at least Grade 1. For laboratory tests with criteria for both increased and decreased levels, analyses for each direction (ie, increased, decreased) will be presented separately.

If there is any laboratory toxicity grading scale overlapping with the normal reference ranges (eg, grade 1 scale overlaps with normal reference ranges), laboratory values that are within the normal range will be grade 0, except for lipid tests.

For triglycerides, LDL, and cholesterol, the protocol-specified toxicity grading scale is for fasting test values, so nonfasting lipid results (or lipid results without a known fasting status) will not be graded or summarized by toxicity grades.

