7.2.2.1. Treatment-Emergent Laboratory Abnormalities

Treatment-emergent laboratory abnormalities are defined as values that increase at least 1 toxicity grade from baseline at any postbaseline time point, up to 30 days after permanent discontinuation of study drug. If the relevant baseline laboratory value is missing, any abnormality of at least Grade 1 observed within the time frame specified above will be considered treatment-emergent. Notice that the baseline toxicity grade for all B/F/TAF analysis will be based on the first dose date of B/F/TAF.

Fasting glucose and nonfasting glucose (including glucose results without a known fasting status) are graded based on different grading scales as specified in the protocol.

Treatment-emergent laboratory abnormalities will be summarized for fasting glucose. Maximum postbaseline grade, instead of treatment-emergent grade, for nonfasting glucose (including glucose results without a known fasting status) will be summarized, as nonfasting glucose was not assessed at baseline visit for most of the subjects; therefore, an abnormality is treatment-emergent or not cannot be determined for these subjects.

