7.2.2.2. Summaries of Laboratory Abnormalities

The following summaries (number and percentage of subjects) for treatment-emergent laboratory abnormalities will be provided by lab test and treatment group; subjects will be categorized according to the most severe postbaseline abnormality grade for a given lab test:

- Treatment-emergent laboratory abnormalities
- Treatment-emergent Grade 3 and 4 laboratory abnormalities
- Treatment-emergent Grade 2, 3 and 4 laboratory abnormalities

For all summaries of laboratory abnormalities, the denominator is the number of subjects with any nonmissing postbaseline values up to 30 days after last dosing date.

A by-subject listing of all treatment-emergent laboratory abnormalities and treatment-emergent Grade 3 or 4 laboratory abnormalities will be provided by subject ID number and visit in chronological order.

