 - a. The (complete) end date is on or after the first dose date, or
 - b. The month and year (or year) of end date is the same as or after the month and year (or year) of the first dose of study drug, or
 - c. End date is completely missing

Events with Completely Missing Onset Date

An AE with a completely missing onset date is defined as TEAE if end date meets any of the criteria specified in 3) above.

22) LDL: Conversions between 2nd and 3rd generations

LDL was analyzed by 2 different assays in the study: 2nd generation (including RCT2394, RCT2312, and RCT2811) and 3rd generation (RCT3870). Samples collected at earlier visits were analyzed using LDL 2nd generation assay. Samples collected at later visits were analyzed using LDL 3rd generation assay. The conversion formulas are as follow:

$$\text{2nd Gen (mmol/L)} = (\text{3rd Gen} - 0.0626)/0.882$$

$$\text{3rd Gen (mmol/L)} = (0.882 \times \text{2nd Gen}) + 0.0626$$

For this analysis, since LDL samples were analyzed by 2nd generation assay at Baseline, we only requested conversion from 3rd generation to 2nd generation.

For the analysis of change from baseline in fasting direct LDL: the sample analyzed by LDL 3rd generation assay will be converted to 2nd generation as a new record with test codes of LIP.LDL.00.02 in raw data. During ADaM stage, a derived parameter code (FLDL2) for “Fasting LDL Cholesterol 2ND GEN Combined” will be generated to pool the records from both original (including test codes RCT2394, RCT2312, and RCT2811) and converted (LIP.LDL.00.02) 2nd generation results to calculate the change from baseline in fasting direct LDL.

For the analysis of toxicity grade for fasting direct LDL: toxicity grade will be based on the Gilead grading results (ie, toxgrg) from original values before conversion. In another words, during ADaM stage, a derived parameter code (FLDLTOX) for “Fasting LDL Cholesterol for Toxicity” will be generated to pool the records from 2nd generation (including RCT2394, RCT2312, and RCT2811) and 3rd generation (ie, RCT3870) to derive treatment-emergent toxicity grades, maximum postbaseline toxicity grades, etc.

23) Correction for Serum creatinine and eGFR (corrected)

1. Calibration lot changed on 01JUL2018 local time.
2. For samples collected on or after 01JUL2018, please use the inverse conversion formula in the below table.
3. The correction is based on unit of umol/L, after correction by regular regression, covert to mg/dL by multiplying 0.0113.

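### Treatment-emergent LDL grades compare a 2nd-generation baseline with unconverted 3rd-generation results, so a rise that is emergent on either single assay scale can go unflagged

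*SAP*

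**What the plan says.** Item 22 of SAP Appendix 6 reports that LDL was measured by a 2nd-generation assay at earlier visits and a 3rd-generation assay at later ones, and gives a conversion formula in each direction. Conversion was requested only from 3rd to 2nd generation, "since LDL samples were analyzed by 2nd generation assay at Baseline". The converted results feed FLDL2, which is used for change from baseline.

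Toxicity is handled differently: "toxicity grade will be based on the Gilead grading results (ie, toxgrg) from original values before conversion". FLDLTOX is then built "to pool the records from 2nd generation (including RCT2394, RCT2312, and RCT2811) and 3rd generation (ie, RCT3870) to derive treatment-emergent toxicity grades", among other grade outputs.

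SAP 7.2.2.1 gives the definition those grades must meet: "Treatment-emergent laboratory abnormalities are defined as values that increase at least 1 toxicity grade from baseline at any postbaseline time point". Protocol 8.6.3 says the same: "values that increase at least 1 toxicity grade from baseline at any time post baseline".

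Three other rules bear on the point.
- SAP 7.2.2 sets in-range results to Grade 0, but with an exemption: "laboratory values that are within the normal range will be grade 0, except for lipid tests". LDL grades therefore depend only on the fixed limits in Protocol Appendix 5.
- SAP Section 3 states: "All table summaries in this final analysis will be based on data included in the All B/F/TAF analysis". Under SAP 3.8.1, subjects who switch from DTG + F/TAF get a new baseline for that analysis.
- SAP 7.2.2.2 carries the flags into listings: "A by-subject listing of all treatment-emergent laboratory abnormalities and treatment-emergent Grade 3 or 4 laboratory abnormalities will be provided".

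**The concern.** Change from baseline and emergent grade are both within-subject comparisons with baseline. Item 22 puts the first on a common scale and leaves the second on mixed scales, without giving a reason. At gradable LDL levels the 3rd-generation assay reads lower, so a baseline graded on the higher-reading assay is set against later samples graded on the lower-reading one. The possible result is an emergent LDL row, and matching listing flags, that omit rises which a consistent comparison would show. The same report will show LDL change on the converted scale, so the two outputs could disagree with nothing to tell the reader why.

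**Working it through.** **Inputs.** From SAP Appendix 6, item 22 (mmol/L): 3rd = 0.882 × 2nd + 0.0626, and 2nd = (3rd − 0.0626)/0.882. From Protocol Appendix 5, adult fasting LDL (mmol/L): Grade 1 is 3.35 to 4.15, Grade 2 is >4.15 to 4.92, Grade 3 is >4.92, and there is no Grade 4.

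**The plan's own figures.** The two formulas are exact inverses of each other, so the stated pair reproduces.

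**Direction.** The scales cross where x = 0.882x + 0.0626, that is at 0.0626/0.118 = 0.53 mmol/L. Above that the 3rd-generation value is the lower one. The lowest graded value is 3.35, so the 3rd-generation assay reads lower at every gradable level.

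**Limits on each scale.**

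| Limit | As a raw 3rd-generation limit, expressed on the 2nd-generation scale: (c − 0.0626)/0.882 | As a 2nd-generation limit, expressed on the 3rd-generation scale: 0.882c + 0.0626 |
|---|---|---|
| 3.35 | 3.73 | 3.02 |
| 4.15 | 4.63 | 3.72 |
| 4.92 | 5.51 | 4.40 |

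**Three comparisons for a subject with a 2nd-generation baseline and a post-switch sample.**
- Planned: baseline graded on the 2nd-generation value, later sample graded on the raw 3rd-generation value.
- Single 2nd-generation scale: same baseline grade, later sample converted. Converting can only keep or raise the later grade, so the planned emergent grade cannot be higher than this one.
- Single 3rd-generation scale: same later grade, baseline converted. Converting can only keep or lower the baseline grade, so again the planned emergent grade cannot be higher.

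**Where the planned flag departs from a consistent 3rd-generation comparison.** This needs a baseline whose grade falls on conversion: about 3.35-3.73, >4.15-4.63 or >4.92-5.51 mmol/L. It also needs a later raw value in the same grade as the unconverted baseline, so that the plan sees no rise.

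**Where the rise is emergent on both single scales and still missed.** The converted later value must also pass the next limit.
- Baseline 3.35-3.73 (Grade 1): later raw value above 3.72 and up to 4.15.
- Baseline >4.15-4.63 (Grade 2): later raw value above 4.40 and up to 4.92.
- Baseline >4.92-5.51 (Grade 3): none, because no higher LDL grade exists on the 2nd-generation scale.

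**Example.** Baseline 3.60 (2nd generation), later raw 3.90 (3rd generation).
- Planned: 3.60 is Grade 1 and 3.90 is Grade 1, so not emergent.
- 2nd-generation scale: (3.90 − 0.0626)/0.882 = 4.35, so Grade 1 to Grade 2, emergent.
- 3rd-generation scale: 0.882 × 3.60 + 0.0626 = 3.24, so Grade 0 to Grade 1, emergent.

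**Grade 0 baseline.** A 2nd-generation value below 3.35 converts to below 3.02, which is still Grade 0. The planned flag then equals a consistent 3rd-generation comparison and can differ only from the 2nd-generation scale. With baseline 3.20 and later raw 3.20, the planned result is Grade 0 to 0. On the 2nd-generation scale the later value is (3.20 − 0.0626)/0.882 = 3.56, Grade 1.

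**Numerical check.** Comparing all three rules over a grid of baseline and later values found no pair in which the planned emergent grade exceeded either single-scale grade. It also confirmed the baseline and raw-value ranges above.

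**The case against.** The strongest reply is that the plan follows a stated and defensible convention. The same laboratory result always receives the same grade, tabulated grades match those the laboratory reported, and regression-converted values are not used to classify individuals against thresholds. Numeric LDL summaries already deal with the assay change. The documents do not say which assay is more accurate or which one the Protocol limits belong to, so a rise seen only on the 2nd-generation scale is not clearly a missed event. That part stands, and it limits the point.

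A reader might infer that every post-switch value between a Protocol limit and its shifted equivalent is a lost event. An example would be 3.70 on the baseline scale reading 0.882 × 3.70 + 0.0626 = 3.33, Grade 0. The documents do not support this. From a Grade 0 baseline, that result is also not emergent on a consistent 3rd-generation scale. The shift in the limits (3.35 to 3.73, and so on) therefore measures the choice of scale, not the mismatch.

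The convention does not answer the baseline ranges in which both consistent comparisons flag a rise and the planned one does not. Stating a rule does not reconcile it with a definition that requires comparison with baseline.

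The effect is also bounded. Item 13 of Appendix 6 counts every post-baseline graded result up to 30 days after the last dose, so another sample at the higher grade removes it. Maximum post-baseline grades use no baseline and are not in question.

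**Conclusion.** The point holds in a limited form. For a subject with a 2nd-generation baseline and a post-switch sample, the planned emergent LDL grade can be lower than on a single scale and never higher. In two baseline ranges it can miss a rise that is emergent whichever single scale is chosen.

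This rests only on the SAP's conversion formulas and the Protocol's LDL limits. The number of affected subjects cannot be computed, since the documents give neither the LDL switch date nor an LDL distribution.

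Two stronger readings should be resisted.
- *Bias towards one displayed group.* Item 22 says baseline was 2nd generation without naming a group, and DTG + F/TAF switchers are re-baselined at extension entry. If those baselines are 2nd generation, both columns are exposed. If they are 3rd generation, that column has no mismatch and the two columns rest on different comparisons. The documents do not settle which.
- *Lost Grade 3 events on any reading.* Emergent Grade 3 on both single scales needs a later raw value above 4.92 and a 2nd-generation baseline no higher than 4.92, and the plan flags that case too. Any Grade 3 difference depends on which scale is preferred.

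No hypothesis test or efficacy result is touched. SAP 7.2 plans no formal testing of laboratory data, so the effect is confined to descriptive safety tables and listings.

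**What to change.** Add one treatment-emergent LDL table, with a matching flag in the by-subject listing, in which baseline and all post-baseline values are on one scale for all subjects in both groups. The simplest route is to regrade FLDL2. Do not regrade only the subjects who span the switch, because one raw result could then carry two different grades in the same row.

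Keep the planned original-value table and the maximum post-baseline grades as they are. Footnote the emergent LDL row with the assay change, the switch date and the number of subjects per group whose baseline is post-switch.

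The cost is a little programming. The converted records already exist, but they must be regraded because toxgrg holds grades of the original values. Grades from converted values may differ from laboratory-reported grades. For subjects whose baseline is itself 3rd generation, the added table can also remove a flag. Raw 3.02 to 3.36 is Grade 0 to 1 as measured, but converts to (3.02 − 0.0626)/0.882 = 3.35 and (3.36 − 0.0626)/0.882 = 3.74, Grade 1 to 1. This is a reason to show the two tables side by side.
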